3 INVESTIGATIONAL PLAN

3.1 Overview of study design

This is a 60-week, prospective, multicenter, randomized, controlled, [REDACTED] pivotal clinical study to investigate the effectiveness and safety of Radiesse (+) to improve the contour of jawline by adding volume to the jawline. Approximately 180 subjects with a grade of 2 or 3 on the MJAS will be enrolled into the study. [REDACTED]

[REDACTED] Subjects will be enrolled at up to 15 sites in the United States. [REDACTED]

At the baseline visit, enrolled subjects will be randomized (2:1 allocation ratio) to either treatment with Radiesse (+) or to untreated control. Those allocated to the control group at baseline will remain untreated until assessment of the primary effectiveness endpoint at Week 12; these subjects will then be eligible for delayed treatment with Radiesse (+) in the jawline at Week 12 and will be followed for 48 weeks post-treatment. [REDACTED]

[REDACTED] Subjects who did not achieve a \geq 1-point improvement on the MJAS [REDACTED] will be required to have a touch-up injection. [REDACTED]

Subjects [REDACTED] may have a touch-up on one or both jawline(s) for further correction at the discretion of the treating investigator and the subject. The primary effectiveness endpoint will be assessed 12 weeks post-treatment. Subjects randomized to the treatment group at baseline will have the option for retreatment with Radiesse (+), upon agreement between the subject and the investigator, at Week 48 and will then be followed for an

additional 12 weeks, for a total study duration of 60 weeks. Subjects who do not receive a retreatment at Week 48 will also be followed until Week 60.

Subjects randomized to the control group at baseline will remain untreated until completion of the primary endpoint assessment at Week 12. After all primary endpoint assessments have been completed these control subjects will be treated with Radiesse (+) (i.e., delayed treatment) and will then be followed 48 weeks post-treatment. Subjects who did not achieve a \geq 1-point improvement on the MJAS [REDACTED]

[REDACTED] will be required to have a touch-up injection [REDACTED]

Subjects who achieve a \geq 1-point improvement on the MJAS [REDACTED]

[REDACTED] may have a touch-up [REDACTED] at the discretion of the treating investigator and the subject. Control subjects will not be offered retreatment.

[figure not shown]
3.2 Study assessments and definitions

[figure not shown]
3.2.1 Effectiveness assessments

[figure not shown]
3.2.1.1 Merz Jawline Assessment Scale (MJAS)

As individuals age, the loss of volume and the descent of the jowl and facial soft tissue creates a defined, contour irregularity with formation of a post-jowl and possibly a pre-jowl defect. The MJAS [REDACTED] was developed to grade the loss of volume and disruption of contour in the jawline region. The 5-point MJAS illustrates the progression of severity.

[REDACTED]

[figure not shown]

[figure not shown]

3.2.1.3 *Treating Investigator Global Aesthetic Improvement Scale (GAIS)*

The treating investigator will use the GAIS to assess global aesthetic improvement among treated subjects [REDACTED].

[figure not shown]

[figure not shown]
Refer to the study endpoints (see [Section 2.2](#)) and visit schedules (see [Sections 5.1.1](#) and [5.1.2](#) [REDACTED]) for additional information regarding the GAIS assessments and the associated reference time points.

3.2.1.4 *Subject Global Aesthetic Improvement Scale (GAIS)*

Treated subjects will evaluate their overall aesthetic improvement on the subject GAIS

[figure not shown]

[figure not shown]
3.2.1.5 *FACE-Q Instruments* [REDACTED]

Treated subjects will evaluate the treatment outcome using [REDACTED] FACE-Q instruments.

[figure not shown]
[REDACTED] With respect to the jawline treatment within this

study, [REDACTED] FACE-Q assessments will be completed by all subjects at baseline and at multiple study visits [REDACTED]
[REDACTED]

3.2.2

3.2.3 Safety assessments

3.2.3.1 72-hour follow-up phone call

Subjects in the treatment group will receive a follow-up phone call 72 hours (\pm 1 day) after the initial treatment at baseline and after the Week 48 retreatment, if applicable. Subjects in the control/delayed-treatment group will receive a follow-up phone call 72 hours (\pm 1 day) after the initial treatment at Week 12.

During this phone call, study personnel will discuss and record any changes in concomitant medications/procedures and confirm that the subject remains compliant with any applicable study restrictions.

[figure not shown]
[REDACTED] f
there are any safety concerns that would necessitate an unscheduled visit to the site, this visit should be scheduled during the phone call.

[figure not shown]
The subjects should also be asked if they are experiencing any new or unusual symptoms related to a potential vascular occlusion (e.g., signs of a stroke, changes in vision, tissue necrosis) as noted in the Study Information Guide for Subjects. If the subjects report any signs or symptoms of a stroke, they must call 911 immediately. If the subjects report any changes in vision associated with vascular occlusion, they must contact the site identified Ophthalmologist prior to contacting the site investigator. If any other symptoms related to a potential vascular occlusion are reported by the subjects, they should be assessed, and referred for immediate medical treatment as deemed necessary per best medical practices. If any change to vision is reported during the 72-hour follow-up phone call, the subject may be asked to come in immediately for an examination or referred immediately to an ophthalmologist for further evaluation.

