5 STUDY PROCEDURES

5.1 Schedule of events by visit

The Schedule of Events, for both treatment and control/delayed-treatment groups, are presented in [Appendices 11.1](#) and [11.2](#), respectively.

5.1.1 Schedule of events by visit for subjects randomized to the treatment group only

Visit 1 – Day 1/Baseline (Screening/Enrollment/Treatment)

The following procedures will be performed at baseline for subjects randomized to the **treatment group**:

Pre-Treatment Assessments:

- Obtain written informed consent. A subject must be informed of the study requirements, including the risks and benefits of participation. An IEC/IRB-approved informed consent must be signed and dated by the subject prior to any study-related activities or procedures being performed, including discontinuation of any prohibited medications.
- Record demographics/medical history [REDACTED]
[REDACTED].
- Record height and weight for BMI.
- Review and record concomitant medications/procedures.
- Perform urine pregnancy test (if female of childbearing potential). Negative test required prior to randomization.

JAS assessments

- Administer FACE-Q assessments to subject.

- Treating physician confirms that the subject meets all eligibility criteria prior to randomization.

Randomization:

- Randomize subject to either the treatment group or control/delayed-treatment group [REDACTED].

Injection (initial treatment):

- Administer treatment injections (see [Section 6.3.1](#) for injection instructions).
- Review and record any AEs (since the time of signing the Informed Consent Form (ICF)).
- Schedule 72-hour follow-up phone call.

Follow-up phone call (72-hours post-treatment): Day 4 (\pm 1 day)

- Discuss and record any changes in concomitant medications/procedures. Confirm subject remains compliant with any applicable study restrictions.
- Discuss and record any AEs.
- If subject reports a safety concern, arrange an unscheduled visit.

- Ask whether the subject is experiencing any new or unusual symptoms related to a vascular occlusion (e.g., signs of a stroke, changes in vision, tissue necrosis) as noted in the Study Safety Information Guide for Subjects.
- If the subject reports any such symptoms, they should be assessed and referred for immediate medical treatment as deemed necessary per best medical practices. If any change to vision is reported, the subject may be asked to come in immediately for an examination or referred immediately to an ophthalmologist for further evaluation.

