
Visit 2 (Week 2 post-treatment): Day 14 (\pm 3 days)

- Review and record changes in any concomitant medications/procedures. Confirm subject remains compliant with any applicable study restrictions.
- Review and record any AEs.

[figure not shown]
Visit 3 (Week 4 post-treatment): Day 29 (+ 3 days)

[figure not shown]
- Review and record changes in any concomitant medications/procedures. Confirm subject remains compliant with any applicable study restrictions.
- Review and record any AEs.

- [REDACTED] MJAS assessment.

[figure not shown]
- Have subject complete the Subject GAIS.

- Administer FACE-Q assessments to subject.

- Administer Treating Investigator GAIS.

Injection (only for subjects who receive a touch-up treatment):

- Perform urine pregnancy test (if female of childbearing potential).
- Administer touch-up injection as follows:
 - If a subject does not achieve a \geq 1-point improvement [REDACTED]

[REDACTED], a touch-up will be required to achieve optimal correction.

- If a subject achieves a \geq 1-point improvement on the MJAS [REDACTED] a touch-up may be done [REDACTED]

Visit 4 (Week 6 post-treatment): Day 42 (\pm 3 days)

Note: This visit is only for subjects who received a touch-up at Week 4.

- Review and record changes in any concomitant medications/procedures. Confirm subject remains compliant with any applicable study restrictions.
- Review and record any AEs.

Visit 5 (Week 12 post-treatment): Day 84 (\pm 3 days)

- Review and record changes in concomitant medications/procedures. Confirm subject remains compliant with any applicable study restrictions.
- Review and record any AEs.

- Record height and weight for BMI.
- [REDACTED] MJAS assessment.

- Have subject complete the Subject GAIS.

- Administer FACE-Q assessments to subject.

- Administer Treating Investigator GAIS.

Visit 6 (Week 24 post-treatment): Day 168 (\pm 10 days)

- Review and record changes in concomitant medications/procedures. Confirm subject remains compliant with any applicable study restrictions.
- Review and record any AEs.
- [REDACTED] MJAS assessment.

- Administer FACE-Q assessments to subject.

- Administer Treating Investigator GAIS.

Visit 7 (Week 36 post-treatment): Day 252 (\pm 10 days)

- Review and record changes in concomitant medications/procedures. Confirm subject remains compliant with any applicable study restrictions.
- Review and record any AEs.
- [REDACTED] MJAS assessment.

- Have subject complete the Subject GAIS.

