- Administer FACE-Q assessments to subject.

- Administer Treating Investigator GAIS.

Visit 8 (Week 48 post-treatment): Day 336 (\pm 10 days)

- Review and record changes in concomitant medications/procedures. Confirm subject remains compliant with any applicable study restrictions.
- Review and record any AEs.
- [REDACTED] MJAS assessment.

- Have subject complete the Subject GAIS.

- Administer FACE-Q assessments to subject.

- Administer Treating Investigator GAIS.

Injection (only for subjects who receive retreatment):

- Perform urine pregnancy test (if female of childbearing potential).
- Retreatment injections may be administered [REDACTED] at the discretion of the treating investigator [REDACTED]
[REDACTED].
- Schedule 72-hour follow-up phone call.

Follow-up phone call (72-hours post retreatment): Day 339 (\pm 1 day)

Note: This phone call is only for subjects who received a retreatment at Week 48.

- Discuss and record any changes in concomitant medications/procedures. Confirm subject remains compliant with any applicable study restrictions.
- Discuss and record any AEs.
- If subject reports a safety concern, arrange an unscheduled visit.

- Ask whether the subject is experiencing any new or unusual symptoms related to a vascular occlusion (e.g., signs of a stroke, changes in vision, tissue necrosis) as noted in the Study Information Guide for Subjects.
- If the subject reports any such symptoms, they should be assessed and referred for immediate medical treatment as deemed necessary per best medical practices. If any change to vision is reported, the subject may be asked to come in immediately for an examination or referred immediately to an ophthalmologist for further evaluation.

Visit 9 (Week 50 post-treatment): Day 350 (\pm 3 days)

Note: This visit is only for subjects who received a retreatment at Week 48.

- Review and record changes in any concomitant medications/procedures. Confirm subject remains compliant with any applicable study restrictions.
- Review and record any AEs.

Visit 10 (Week 60 post-treatment)/ End of Study/Early Termination: Day 420 (\pm 10 days)

- Review and record changes in concomitant medications/procedures. Confirm subject remains compliant with any applicable study restrictions.
- Review and record any AEs.
- Record height and weight for BMI.
- Perform urine pregnancy test (if female of childbearing potential).
- [REDACTED] MJAS assessment.

- Have subject complete the Subject GAIS.

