- [REDACTED]
- Ask whether the subject is experiencing any new or unusual symptoms related to a vascular occlusion (e.g., signs of a stroke, changes in vision, tissue necrosis) as noted in the Study Information Guide for Subjects.

- If the subject reports any such symptoms, they should be assessed and referred for immediate medical treatment as deemed necessary per best medical practices. If any change to vision is reported, the subject may be asked to come in immediately for an examination or referred immediately to an ophthalmologist for further evaluation.

Visit 4 - Week 14 (2 weeks post-treatment): Day 14 (\pm 3 days)

- Review and record changes in any concomitant medications/procedures. Confirm subject remains compliant with any applicable study restrictions.
- Review and record any AEs.

[figure not shown]
Visit 5 – Week 16 (4 weeks post-treatment): Day 29 (+ 3 days)

[figure not shown]
- Review and record changes in any concomitant medications/procedures. Confirm subject remains compliant with any applicable study restrictions.
- Review and record any AEs.

- [Redacted] MJAS assessment.

- Have subject complete the Subject GAIS.

- Administer FACE-Q assessments to subject.

- Administer Treating Investigator GAIS.

Injection (only for subjects who receive a touch-up treatment):

- Perform urine pregnancy test (if female of childbearing potential).
- Administer touch-up injection as follows:
 - If a subject does not achieve a \geq 1-point improvement [REDACTED]
[REDACTED], a touch-up will be required [REDACTED].
 - If a subject achieves a \geq 1-point improvement on the MJA [REDACTED]
[REDACTED] a touch-up [REDACTED] may be don [REDACTED]

Visit 6- Week 18 (6 weeks post-treatment): Day 42 (\pm 3 days)

Note: *This visit is only for subjects who received a touch-up at Visit 5.*

- Review and record changes in any concomitant medications/procedures. Confirm subject remains compliant with any applicable study restrictions.
- Review and record any AEs.

Visit 7- Week 24 (12 weeks post-treatment): Day 84 (\pm 3 days)

- Review and record changes in concomitant medications/procedures. Confirm subject remains compliant with any applicable study restrictions.

- Review and record any AEs.

[REDACTED]

- Record height and weight for BMI.
- [REDACTED] MJAS assessment.

[REDACTED]

- Have subject complete the Subject GAIS.

[REDACTED]

- Administer FACE-Q assessments to subject.

[REDACTED]

- Administer Treating Investigator GAIS.

[REDACTED]

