6.3 Study treatment

All protocol-specific criteria for the administration of study treatment must be met and documented prior to administration of any study treatment. All device administration (injection) will be performed on site by the treating investigator. Subjects will not be dispensed any investigational material. Any noncompliant subject or site may be discontinued from the study (see [Section 5.2](#)).

6.3.1 *Planned treatment procedure and administration*

Approximately 120 subjects will be randomized to receive Radiesse (+) and 60 subjects will serve as the controls/delayed treatment. Subjects will be randomized using a 2:1 allocation ratio for treatment to control.

Subjects randomized to treatment at baseline will receive an initial Radiesse (+) injection in both jawlines.

Subjects who do not achieve a \geq 1-point improvement on the MJAS [REDACTED] will be required to have a touch-up injection [REDACTED]. [REDACTED] the treating investigator will be responsible for establishing whether the \geq 1-point MJAS improvement threshold is met [REDACTED]

In addition, subjects who achieve a \geq 1-point improvement on the MJAS [REDACTED] may have a touch-up [REDACTED] at the discretion of the treating investigator and the subject. These subjects are also eligible for retreatment at Week 48 if the subject and investigator are in agreement that retreatment is needed. [REDACTED]

After completion of all study assessments associated with the primary endpoint at Week 12, subjects randomized to the control group will be treated with Radiesse (+) (i.e., delayed treatment).

Subjects who did not achieve a \geq 1-point improvement on the MJAS [REDACTED] will be required to have a touch-up injection [REDACTED]. [REDACTED]

the treating investigator will be responsible for establishing whether the \geq 1-point MJAS improvement threshold is met [REDACTED]

In addition, subjects who achieve a \geq 1-point improvement on the MJAS [REDACTED] may have a touch-up [REDACTED] at the discretion of the treating investigator and the subject. [REDACTED]

6.3.1.1 *Jawline region and treatment area*

[figure not shown]
All study injections will be performed by the site's principal investigator (PI). The PI is also described as the treating investigator in this document.

Observed adverse events will also be recorded.

The jaw region is defined as follows:

- Anterior to posterior boundaries: from the anterior aspect of the pre-jowl sulcus to just anterior to the earlobe.

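### The 72-hour safety call follows every injection session except the touch-up, where the first scheduled contact comes 7 to 16 days later

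*Protocol*

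**What the plan says.** Protocol Section 3.2.3.1 lists the occasions for the 72-hour (±1 day) call. Treatment-group subjects are called "after the initial treatment at baseline and after the Week 48 retreatment, if applicable". Control subjects are called after their first treatment at Week 12. During the call, staff ask about symptoms of vascular occlusion such as stroke signs, vision changes and tissue necrosis.

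The visit schedules in Section 5.1 agree with that list:

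- **Initial treatment (5.1.1):** a step to book the call, then the entry "Follow-up phone call (72-hours post-treatment): Day 4", then a Week 2 visit on Day 14.
- **Week 48 retreatment (5.1.1):** a step to book the call, then a call on Day 339 with the note "This phone call is only for subjects who received a retreatment at Week 48", then "Visit 9 (Week 50 post-treatment): Day 350".
- **Delayed treatment, control group (5.1.2):** the call on post-treatment Day 4, then a visit on Day 14.
- **Touch-up:** under "Administer touch-up injection as follows", the readable steps at Visit 3 (5.1.1) and Visit 5 (5.1.2) contain no booking step and no call entry follows. The next contact is a dedicated visit on Day 42: for the treatment group "This visit is only for subjects who received a touch-up at Week 4", and for the control group "This visit is only for subjects who received a touch-up at Visit 5".

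Section 6.3.1.2 lists the touch-up among the injection sessions. Under Section 6.3.1, a subject below the 1-point MJAS threshold "will be required to have a touch-up injection".

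**The concern.** Section 1.2 ties the most serious risk, unintended placement of product in a vessel, to the injection itself. The protocol answers that risk with an early, prompted contact after each session except the touch-up, and the readable text gives no reason for the exception. Some subjects have a touch-up because the protocol requires it.

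Two things are at stake.

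- **Safety.** After a touch-up, no one from the site is scheduled to ask about vascular symptoms in the first days. The readable content of the Day 42 visit is a review of adverse events and concomitant treatments, without the scripted vascular questions.
- **Data.** Section 1.2 says common injection reactions have generally resolved within seven days. Most touch-up reactions would therefore be over by the only scheduled contact and would be recorded from recall. Section 8.4.2 plans event counts, durations and severities, and summaries by need for touch-up, so early ascertainment would differ along a factor that the safety tables report.

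**Working it through.** The plan gives no figure to reproduce here. The check matches each injection session to its scheduled contacts and takes differences between visit windows.

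**Inputs (Protocol Sections 3.2.3.1, 5.1.1, 5.1.2)**

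- Touch-up visit: Day 29 (+3), so Day 29 to 32 in both groups, counted from first treatment.
- Touch-up follow-up visit: Day 42 ±3, so Day 39 to 45 in both groups.
- Call after initial or delayed treatment: Day 4 ±1, with treatment on Day 1.
- Call after retreatment: Day 339 ±1, with retreatment nominally on Day 336.
- Two-week visits: Day 14 after initial treatment, Day 350 after retreatment.

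**First scheduled contact after a touch-up**

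- Shortest: earliest follow-up minus latest touch-up = 39 − 32 = 7 days.
- Longest: latest follow-up minus earliest touch-up = 45 − 29 = 16 days.
- Nominal: 42 − 29 = 13 days.

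**First scheduled contact after the other sessions**

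- Initial or delayed treatment: 4 − 1 = 3 days.
- Retreatment: 339 − 336 = 3 days.
- With the ±1 day window: 3 − 1 = 2 to 3 + 1 = 4 days.

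**Does the Day 42 visit stand in for the call?**

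| Session | Call (nominal) | Two-week visit (nominal) |
|---|---|---|
| Initial or delayed treatment | 3 days | 14 − 1 = 13 days |
| Touch-up | none | 42 − 29 = 13 days |
| Week 48 retreatment | 3 days | 350 − 336 = 14 days |

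The touch-up visit matches the two-week visit that the other sessions have in addition to the call.

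**Coverage**

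- By type of session, three of five have a call (baseline, Week 48, delayed Week 12). The two touch-ups (Week 4, Week 16) do not.
- Per subject with a touch-up, the session without a call is 1 of at most 3 in the treatment group and 1 of 2 in the control group.
- The touch-up rate is not visible, so the number of affected sessions cannot be calculated.

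**Sensitivity.** The touch-up window is printed as +3 days in both groups. If ±3 were meant, the longest gap would be 45 − 26 = 19 days and the shortest would stay at 7.

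**The case against.** The strongest reply is that this is a consistent design choice. Section 3.2.3.1 and the schedules agree, and the protocol did consider touch-up safety, since each group has a visit solely for touch-up subjects. There are other safeguards: a written symptom list with instructions to act at once (3.2.3.2), unscheduled safety visits (5.1.4), a 24-hour phone number and named specialist contacts in the consent form (9.2), and a scripted call about four weeks earlier. The call comes 2 to 4 days after injection, so even where it exists it is a backstop and not the means of emergency detection. Touch-up extent is redacted and may involve one jawline only, so equal risk per session is not shown.

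Part of this stands. No contradiction or broken commitment is involved. The call is a second layer, and subjects are well instructed. Equal risk per session cannot be claimed. The effect on data is plausible but cannot be sized: reactions can still be entered at Day 42 with start and stop dates, and a redacted collection tool might already capture them.

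It does not remove the point. The listed safeguards depend on the subject making contact, and they apply equally after initial treatment and retreatment, where the protocol still schedules a call. Retreated subjects have also had an earlier call, and they are called again. A call hidden by redaction is unlikely, because the list in Section 3.2.3.1 is readable and each of the other calls has its own visible entry.

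**Conclusion.** The concern holds. In the readable text, first scheduled contact after a touch-up is nominally 13 days away, 10 days later than after any other session (13 − 3). The missing element is the early, site-initiated contact with its vascular questions.

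This should be corrected, but it does not threaten the validity of the trial. The effectiveness analysis is untouched. Subject-level incidence of related events should be little affected, because every touch-up subject has already had a first treatment with its call. The exposure in the data is a possible undercount of early touch-up reactions in the event tallies.

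Confidence is high that the call is missing from the readable plan and lower on the size of the data effect. The conclusion assumes that the printed windows are as intended and that no redacted text or unseen appendix adds a touch-up call.

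**What to change.** Three edits are needed.

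1. In Section 3.2.3.1, add the touch-up, in both groups, to the occasions for the 72-hour (±1 day) call, with the existing script.
2. In Section 5.1.1 Visit 3 and Section 5.1.2 Visit 5, add a step under the touch-up injection to book the call, followed by a call entry like those after the other sessions.
3. Carry the call into the schedules in Appendices 11.1 and 11.2, timed from the actual touch-up date. For a touch-up on Day 29 this is 29 + 3 = Day 32, ±1.

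First scheduled contact after a touch-up then falls at 2 to 4 days, as after the other sessions. The Day 42 visit stays as it is.

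The cost is one short call per touch-up subject, by staff who already make these calls. The maximum rises from 2 to 3 calls per treatment-group subject and from 1 to 2 per control subject. Even if every planned subject had a touch-up, that is about 120 + 60 = 180 extra calls. No visit, assessor or procedure is added.
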